WOCBP	Women of Child Bearing Potential

1. INTRODUCTION

1.1. BACKGROUND

“Dry eye disease, (DED) is a multifactorial disease of the ocular surface characterized by a loss of homeostasis of the tear film, and accompanied by ocular symptoms, in which tear film instability and hyperosmolarity, ocular surface inflammation and damage, and neurosensory abnormalities play etiological roles” ([Craig 2017](#)).

In a recent review of the large volume on literature, “the prevalence of DED ranged from 5 to 50%. The prevalence of signs was higher and more variable than symptoms...”. “...Women have a higher prevalence of DED than men, although differences become significant with age. Risk factors were categorized as modifiable/nonmodifiable, and as consistent, probable or inconclusive...”. “...The economic burden and impact of DED on vision, quality of life, work productivity, psychological and physical impact of pain, are considerable, particularly costs due to reduced work productivity” ([Stapleton 2017](#)).

One group of experts concluded that the mechanisms involved in the initiation and perpetuation of dry eye disease are evaporative water loss leading to hyperosmolar tissue damage. “Research in human disease and in animal models has shown that this, either directly or by inducing inflammation, causes a loss of both epithelial and goblet cells. The consequent decrease in surface wettability leads to early tear film breakup and amplifies hyperosmolarity via a Vicious Circle. Pain in dry eye is caused by tear hyperosmolarity, loss of lubrication, inflammatory mediators and neurosensory factors, while visual symptoms arise from tear and ocular surface irregularity” ([Bron 2017](#)).

There are overlapping etiologies of aqueous deficient and evaporative dry eye. While evaporative dry eye may be more prevalent than aqueous deficient DED, as the disease progresses, both sources become apparent ([DEWS II](#)). In both groups, desiccating stress ultimately results in ocular surface inflammation ([Stevenson 2012](#)).

Given this pathophysiology, many approaches have been tried in the pharmacological treatment of DED. Approved pharmacotherapies in the U.S. include the immunomodulator cyclosporine (Restasis®, Cequa®) and the lymphocyte function-associated antigen-1 (LFA-1) antagonist, lifitegrast (Xiidra®). As well, medical devices marketed in the U.S. for treatment of DED and other ocular surface disorders include a nasal neurostimulatory device (TrueTear®) and warming of the eyelids (LipiFlow®). While safe and effective, not all patients with DED are fully served by these current therapies. Thus, there is a need for novel therapies to more broadly serve the needs of patients with this challenging disease.

1.2. STUDY RATIONALE

VivaVision is developing VVN001, a small-molecule antagonist of lymphocyte function-associated antigen 1 (LFA-1) for the treatment of dry eye disease. VVN001 binds to (LFA-1, also known as CD11a/CD18), found on the cell surface of leukocytes. The binding blocks the interaction of LFA-

1 to its cognate ligand, intercellular adhesion molecule-1 (ICAM-1, also known as CD54), typically expressed on endothelial cells and cells of the immune system (T cells and B cells ([Smith 2007](#))).

One antagonist, lifitegrast has been approved for the treatment of dry eye disease. The clinical trials of lifitegrast showed that antagonizing the interaction of LFA-1 and ICAM-1 significantly improved both the symptoms and the signs of the disease. VVN001 is more potent than lifitegrast in antagonizing the LFA-1/ICAM-1 interaction. In addition, VVN001 showed better water solubility (13% weight/volume) than lifitegrast (~5%) at neutral pH. Better water solubility may result in greater ocular comfort upon instillation.

1.3. RISK/BENEFIT ASSESSMENT

Safety data from the pre-clinical studies with VVN001 demonstrate an excellent safety and tolerability profile. LFA-1/ICAM-1 antagonists (lifitgrast) have been studied and approved for human use and prior clinical trials with lifigraast have demonstrated no long-term safety issues with administration. Given the experience with this product in pre-clinical studies as well as with similar approved products used in a dry eye population, there is a favorable benefit-risk ratio. Further the risks of this trial will be mitigated via routine monitoring and reporting of potential new adverse events.

2. STUDY OBJECTIVES AND ENDPOINTS

2.1. OBJECTIVES

The objectives of this study are to:

1. Evaluate the safety and tolerability of VVN001, 1% ophthalmic solution and VVN001, 5% ophthalmic solution when administered BID compared to vehicle administered BID.
2. Evaluate the efficacy activity of VVN001, 1% ophthalmic solution and VVN001, 5% ophthalmic solution administered BID compared to vehicle administered BID in the treatment of signs and symptoms of DED.

2.2. STUDY ENDPOINTS

2.2.1. Safety Endpoints

- Ocular and non-ocular adverse events
- Slit-lamp Biomicroscopy and external eye exam
- Conjunctival hyperemia score
- IOP
- Dilated Ophthalmoscopy
- BCVA
- Drop Comfort/Tolerability Assessment

2.2.2. Primary Efficacy Endpoint:

Mean Change from baseline (Visit 2) to Day 84 (Visit 6) in inferior region of CFS (**iCFS**) using the modified NEI/Industry Workshop (0-4 scale, using 0.5 unit increments)

2.2.3. Secondary Efficacy Endpoints:

The secondary endpoints will be evaluated in a hierarchical fashion and tested sequentially starting with the key secondary endpoint:

Key Secondary Endpoint:

1. Mean Change from baseline (Visit 2) to Day 84 (Visit 6) in the individual symptom of eye dryness (0 – 100 VAS scale).

Other Secondary Endpoints:

1. Mean Change from baseline (Visit 2) to Days 14 (Visit 3), 28 (Visit 4), 56 (Visit 5) and 84 (Visit 6) in total CFS (**tCFS**) using the modified NEI/Industry Workshop (0-20 scale; using 0.5 unit increments)
2. Mean Change from baseline (Visit 2) to Days 14 (Visit 3), 28 (Visit 4), Day 56 (Visit 5) and Day 84 (Visit 6) in each **individual subregion** (inferior (except for Day 84), superior, nasal, temporal, and central) of CFS using modified NEI/Industry Workshop (0-4 scale; using 0.5 unit increments)

3. Mean Change from baseline (Visit 2) to Days 14 (Visit 3), 28 (Visit 4) and 56 (Visit 5) in the individual symptom of eye dryness (0-100 VAS scale)
4. Mean Change from baseline (Visit 2) to Days 14 (Visit 3), 28 (Visit 4) 56 (Visit 5) and 84 (Visit 6) in the individual symptom of eye discomfort (0-100 VAS scale)
5. Mean Change from baseline (Visit 2) to Days 14 (Visit 3), 28 (Visit 4), 56 (Visit 5) and Day 84 (Visit 6) in SANDE.
6. Mean Change from baseline (Visit 2) to Days 14 (Visit 3), 28 (Visit 4), 56 (Visit 5) and Day 84 (Visit 6) in Schirmer

3. STUDY DESIGN

3.1. OVERALL DESIGN OF THE STUDY

This is a Phase 2a, multi-center, double-masked, randomized, vehicle-controlled, parallel-group study designed to evaluate the safety and tolerability and to explore the efficacy activity of VVN001 Ophthalmic solution versus vehicle in subjects with dry eye disease. The study will consist of two periods over 14-weeks total as follows:

1. Screening/ run-in period (Day -14 to Day -1)
2. Treatment period (Day 1 to Day 84)

Screening/Run-In Period:

At Visit 1 Screening (Day 1 minus 14 days), subjects who meet screening inclusion/exclusion criteria will begin a two-week run-in period during which they will be treated with 1 drop of single-masked vehicle per eye in each eye BID for a 14-day run-in period.

Treatment Period:

[figure not shown]
At Visit 2 Randomization (Day 1), subjects who continue to meet inclusion/exclusion criteria will be eligible for randomization to VVN001 Ophthalmic solution or vehicle.

Approximately 165 subjects will be randomized in this study at approximately 10 centers located in the United States (US). Subjects will be randomized to one of the following 3 treatment groups in a 1:1:1 ratio as follows:

- Group A: 1% VVN001 administered BID (morning/evening)
- Group B: 5% VVN001 administered BID (morning/evening)
- Group C: Vehicle administered BID (morning/evening)

Following randomization, subjects will be instructed to self-administer 1 drop of IP per eye into each eye twice daily (morning/evening; Groups A, B, and C). Subjects will be instructed to return to the clinic to be evaluated at Study Visits 3, 4, 5 and 6 (Days 14, 28, 56 and 84 respectively). Subjects must take their morning eyedrop prior to Study Visits 3, 4 and 5. The last dose of IP and the final treatment visit (Visit 6) will occur upon completion of 84 days of treatment. Subjects will be instructed not to use any topical eyedrops (e.g., over the counter artificial tears or topical ocular medications) other than the study medication during the study. Subjects will be released from the study at the end of Visit 6 (Day 84). See [Figure 2](#) for a Schematic of the study visits.

Figure 2

Safety Assessments

Safety assessments in the study will be evaluated in both eyes (OU) and will include:

- Biomicroscopy and external eye exam
- Dilated ophthalmoscopy
- Intraocular pressure (IOP) measurement
- Best Corrected Visual Acuity (BCVA)
- Conjunctival Hyperemia Evaluation
- Drop Comfort/Tolerability Assessment

Efficacy Assessments

Efficacy assessments in the study will be evaluated OU for signs and symptoms of DED and will include:

Signs

- Total CFS score (0 – 20 point scale [using 0.5 increments] scale) at each clinic visit.
- Inferior subregion corneal staining score (0-4 point scale [using 0.5 increments]) at each clinic visit.
- CFS score by each individual (central, temporal, nasal and superior) subregion (0-4 point scale [using 0.5 increments]) at each clinic visit.

- Tear production (Schirmer test without anesthesia, mm/5 min) at each clinic visit.

Symptoms (subject-reported)

- Eye dryness score (0-100 point VAS) evaluated at each clinic visit.
- Eye discomfort score (0-100 point VAS) evaluated at each clinic visit.
- Symptom Assessment Questionnaire iN Dry Eye (SANDE) will be administered at each clinic visit.

3.2. END OF STUDY DEFINITION

A participant is considered to have completed the study if he or she has completed all phases of the study including Visit 6 and has completed procedures shown in the Schedule of Procedures and Assessments ([Appendix 1](#)).

4. STUDY POPULATION

4.1. INCLUSION CRITERIA

At Visit 1 (Screening) and Visit 2 (Randomization) male or female subjects must meet the following criteria:

1. Provide written informed consent prior to any study-related procedures and provide Health Insurance Portability and Accountability Act (HIPAA) authorization.
2. Are 18 years of age or older.
3. Are willing and able to follow instructions and willing to be present for the required study visits for the duration of the study.
4. Have a BCVA, using corrective lenses if necessary, in the qualifying eye(s) of +0.7 or better as assessed by Early Treatment of Diabetic Retinopathy Study (ETDRS) at the screening visit and randomization visits.
5. If a woman of child-bearing potential (WOCBP) not pregnant or lactating and not sexually active (i.e. abstinent) for 14 days prior to Visit 1 and willing to remain so through 30 days following Visit 6 or the last administration of the IP. Alternatively, a WOCBP who is not abstinent must have been using acceptable methods of birth control.
6. Are women who have undergone one of the following sterilization procedures at least 6 months prior to Visit 1:
 - a. Bilateral tubal ligation
 - b. Hysterectomy
 - c. Bilateral oophorectomy
7. Have a history of dry eye disease in both eyes supported by a previous clinical diagnosis or have a self-reported history of subjective complaints for at least 6 months prior to screening
8. Are currently using artificial tears and have been using within 30 days of the screening Visit.
9. Have an Eye dryness score ≥ 40 at Visit 1 and ≥ 35 at Visit 2, one score for both eyes (0-100 point VAS)
10. Have ongoing dry eye disease in the same eye or both eyes, as defined by all of the following criteria at Visit 1 and Visit 2:
 - a. Inferior CFS (iCFS) score of ≥ 2 (NEI; 0-4 scale; using 0.5 unit increments)
 - b. Have a Schirmer score (without anesthesia) of ≥ 1 and ≤ 7 mm/5 min.
11. Have in the opinion of the Investigator, normal lid anatomy.
12. Are willing to withhold artificial tears for the duration of the study.

4.2. EXCLUSION CRITERIA

At Visit 1, for subjects to be eligible for study participation they may not:

1. Have a known hypersensitivity or contraindication to the IP or IP components.
2. Have a Schirmer score (without anesthesia) of <1 or >7mm/5 min in the study eye.
3. Within 14 days prior to screening (Visit 1) have taken:
 - a. Topical ocular antibiotics or systemic antibiotics taken for an ocular condition.
 - b. Serum tears
 - c. Topical ocular non-steroidal anti-inflammatory drugs (NSAIDs)
 - d. Topical ocular or oral antihistamines or mast cell stabilizers
 - e. Topical ocular or nasal vasoconstrictors (Phenylephrine as part of an ocular evaluation is allowed)
4. Within 30 days prior to screening (Visit 1) have taken/used:
 - a. Ocular, inhaled, dermatologic or intranasal corticosteroids
 - b. Topical cyclosporine (Restasis® and Cequa®)
 - c. Topical ophthalmic lifitegrast (Xiidra®)
 - d. Intranasal Tear Neurostimulation
 - e. Any topical ophthalmic medications or makeup for eyelash growth.
5. Have any prior use of isotretinoin (Accutane®).
6. Within 60 days prior to screening (Visit 1), or during the study, have altered the dosage or anticipate alterations to the dose of the following:
 - a. Anticholinergics (if used on a chronic basis)
 - b. Antidepressants (if used on a chronic basis)
 - c. Systemic immunosuppressive agents
 - d. Oral contraceptives
 - e. Oral or injectable corticosteroids (e.g., prednisone. Prednisone dose must be less than 11 mg/day)
7. Expect to use any Cannabidiol products during the study.
8. Have history of uncontrolled glaucoma in either eye, IOP over 21 mmHg at the screening visit or are being treated with eye drops for glaucoma in either eye. Or the subject has had laser or surgery for glaucoma in the study eye within 90 days of the study.
9. Subjects who cannot suspend the use of contact lenses from Visit 1 and throughout the study.

10. Subjects who have a history of Anterior Basement Membrane Corneal Dystrophy.
11. Subjects who have had a corneal transplant or similar corneal surgery (DALK, DSEK, DMEK, etc.).
12. History of incisional ocular surface surgery, including but not limited to refractive, LASIK, Pterygium surgery within 6 months prior to Visit 1.
13. Any incisional intraocular surgical procedure within 12 months prior to Visit 1; or any planned ocular surgical procedure during the study period.
14. History of yttrium aluminum garnet-laser posterior capsulotomy or any laser ocular surgery in past 90 days prior to Visit 1.
15. Non-compliance (<80%) with Vehicle Run-In administration.
16. Have had eyelid surgery within the past 6 months.
17. Have a congenitally absent lacrimal gland or meibomian glands.
18. Have had cauterization of the punctum or have had non-dissolvable (silicone) or short term dissolvable punctal plugs inserted or removed within the 30 days prior to the screening or planned during the study. Have had long-term dissolvable plugs within 3 months of Visit 1.
19. Subjects who have active or have had an outbreak of herpetic keratitis within one year of Visit 1 or subjects who are on chronic oral antivirals for herpetic disease.
20. Have a diagnosis of:
 - a. Ongoing ocular infection, lid margin disorders such as blepharitis (including staphylococcal, demodex or seborrheic) are allowed if not requiring treatment with ocular or systemic antibiotics at Visit 1 or intended treatment during the study.
 - b. Meibomian gland disease requiring mechanical meibomian gland expression within the past 3 months
 - c. Excessive lid laxity, floppy eyelid syndrome, ectropion, entropion in either eye, or moderate to severe pinguecula or pterygia in the study eye per the opinion of the Investigator.
 - d. Stevens-Johnson syndrome
 - e. Significant conjunctival scarring in the judgment of the Investigator
 - f. Severe/serious ocular condition that in the judgment of the Investigator opinion could confound study assessments or limit compliance.
 - g. Severe/serious systemic disease or uncontrolled medical condition that in the judgment of the Investigator could confound study assessments or limit compliance.
21. Have a documented history of ocular allergies, which, in the judgment of the Investigator, are likely to have an acute increase in severity due to the expected timing of the exposure to the allergen to which the subject is sensitive. Subjects sensitive to seasonal allergens that are not expected to be present during the study are permitted.

22. Be current cigarette smokers.
23. Have been exposed to an investigational drug within the preceding 30 days or previously randomized in this study.
24. Be an employee of the site that is directly involved in the management, administration, or support of this study or be an immediate family member of the same.
25. Have a known history of alcohol and/or drug abuse within the past 5 years.
26. In the opinion of the Investigator or study coordinator, be unwilling or unable to comply with the study protocol or unable to successfully instill eye drops.

4.3. RANDOMIZATION CRITERIA

At the Randomization Visit (Visit 2), an eligible subject must continue to meet all clinical inclusion/exclusion criteria as defined in Sections 4.1 and 4.2 with the exception of the Eye dryness score: Eye Dryness ≥ 35 one score for both eyes (0-100 point VAS) will qualify. Note: Subjects must meet all eye specific criteria from Visit 2 in the same qualifying eye as in Visit 1.

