6. STUDY PROCEDURES

6.1. VISIT DESCRIPTIONS

6.1.1. Visit 1 (Screening): Day minus 14 (± 2 days) prior to Visit 2

The following will be performed/assessed in the order suggested below and all ocular assessments will be conducted in both eyes (as applicable):

- Explain the purpose and conduct of the study to the subject, answer the subject's questions, and obtain written informed consent.
- Obtain information including demographics, concomitant medications, ocular and systemic medical and medication history and surgical history.*
- Assess for prior AT use.
- Evaluate eligibility
- A Screening Identification (ID) should be assigned to the Subject once any Visit 1 procedures (other than Informed Consent Form (ICF)) are performed.
- Subject-rated symptom assessments (in this order):
 - Individual eye dryness and discomfort symptom assessment via VAS
 - SANDE
- Urine Pregnancy Test (UPT) for all eligible women of childbearing potential.*
- Safety Lab Draw (Hematology, Serum Chemistry, Serology and Urinalysis).*
- BCVA
- Slit-lamp biomicroscopy and external eye exam
 - Includes evaluation of conjunctival hyperemia
- CFS (Wait 15 minutes prior to performing Schirmer test)
- Unanesthetized Schirmer test
- IOP
- Dilated Ophthalmoscopy
- Determine if the subject is eligible to continue in the study. Do not continue screening any subject who does not meet eligibility requirements. Any subject who does not meet eligibility requirements will be designated as a Screen Failure.
- If the subject is qualified, a kit containing a two-week supply of Single-Masked Run-In will be provided.
- Subject will self-administer first dose of Single-Masked IP observed by trained study staff.
- Administer the Drop Comfort Tolerability Assessment at 1-minute and 5-minutes post dose.

- Dispense daily dosing diary.
- Instruct the subject to discontinue using all prohibited medications for the remainder of the study and schedule to return to the clinic for Visit 2 in two weeks.

*May be performed at any time during the visit in order to facilitate subject and site schedules.

6.1.2. Visit 2 (Randomization): Day 1

Visit 2 will occur 14 (± 2 days) after Visit 1 (Screening). The following will be performed/assessed in both eyes (as applicable):

- Evaluate continued eligibility
- Subject-rated symptom assessments (in this order):
 - Individual eye dryness and eye discomfort symptom assessment via VAS
 - SANDE
- Use of any concomitant medications since the last visit

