- Occurrence of any AEs since the last visit *
- BCVA
- Slit-lamp biomicroscopy and external eye exam
 - Includes evaluation of conjunctival hyperemia
- CFS
- Wait 15-20 minutes after CFS before proceeding
- Unanesthetized Schirmer test
- IOP
- Collect used Run-In, Daily Dosing Diary and check compliance
- Determine if subject is eligible for randomization

For eligible subjects, the following is the process regarding administration of Double-Masked IP whereby the trained site staff will conduct the following procedures:

- Enter subject information into IWRS to determine randomization code and Kit Number.
- Subject will self-administer first dose of Double-Masked IP observed by trained study staff.
- Administer the Drop Comfort/Tolerability Assessment at 1-minute and 5-minutes post dose.

- Assess for occurrence of any IP related AEs
- Dispense 4 weeks supply of double masked IP and Daily Dosing Diary
- Collect used Single-Masked IP kit
- Schedule the subject to return for Visit 3 (Day 14±2 days)

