6.1.7. Early Termination Visit

In the event of termination prior to Visit 6, every attempt will be made to ensure that all the Visit 6 assessments are performed in both eyes at the Early Termination Visit prior to discharge from the study.

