4.8.3. Laboratory Data

Safety laboratory tests will be collected in the central laboratory at Visit 1 and Visit 6. The actual continuous value and change from Visit 1 to Visit 6 will be summarized for each clinical laboratory parameter, including hematology, clinical chemistry, and urinalysis . All laboratory data will be provided in data listings. Urine pregnancy test results will be captured at Visit 1 and Visit 6. Urine pregnancy test results will be provided in data listing.

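### No pregnancy test is scheduled at randomization, although the not-pregnant criterion must hold there; the only pre-dose test falls 12-16 days before the first possible VVN001 dose

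*Protocol*

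**What the plan says.** Protocol Section 4.1 opens its inclusion list with "At Visit 1 (Screening) and Visit 2 (Randomization) male or female subjects must meet the following criteria". Inclusion 5 begins "If a woman of child-bearing potential (WOCBP) not pregnant or lactating and not sexually active (i.e. abstinent) for 14 days prior to Visit 1". The abstinence is to last until 30 days after Visit 6 or the last dose. A woman who is not abstinent must have been using acceptable birth control. Section 4.3 adds that at randomization "an eligible subject must continue to meet all clinical inclusion/exclusion criteria as defined in Sections 4.1 and 4.2", with an exception for the eye dryness score alone.

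The procedures are as follows:

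- **Visit 1 (Section 6.1.1):** "Urine Pregnancy Test (UPT) for all eligible women of childbearing potential".
- **Visit 2 (Section 6.1.2):** no pregnancy test. The list has a general check of continuing eligibility and, before IWRS entry, "Determine if subject is eligible for randomization". The first double-masked dose is then taken in the clinic.
- **Visit 6 (Section 6.1.6):** urine pregnancy test.
- **Early termination (Section 6.1.7):** "every attempt will be made to ensure that all the Visit 6 assessments are performed in both eyes at the Early Termination Visit".

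The pregnancy test rows of Protocol Appendix 1 and SAP Table 1 are marked at Visits 1 and 6 only. SAP Section 4.8.3 agrees: "Urine pregnancy test results will be captured at Visit 1 and Visit 6". Section 3.1 states that the run-in product is vehicle.

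**The concern.** The single pre-dose test guards the start of vehicle, not the start of VVN001. By the time a woman can first receive active drug, her last result is about two weeks old. A pregnancy that was too early to show at Visit 1 may by then be detectable, but nothing in the Visit 2 list would detect it. She would be randomized with a two-in-three chance of an active arm. The next scheduled test is at Day 84, or at an early termination visit.

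The eligibility measures with an objective or scored result (visual acuity, eye dryness, inferior staining, Schirmer) are all taken again at Visit 2. Pregnancy also has a simple objective test, yet at Visit 2 it rests on history.

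Only participant safety is at stake. The documents do not give the size of any fetal risk; Protocol Section 4.7.2 refers to the Investigator's Brochure for toxicology.

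**Working it through.** **Inputs from the documents**

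- Visit 1 to Visit 2: 14 ± 2 days (Protocol Section 6.1.2), so R = 12 to 16 days.
- First possible VVN001 dose: in clinic at Visit 2 (Section 6.1.2).
- Visit 6: Day 84 ± 2, that is Day 82 to 86, with Visit 2 as Day 1 (Section 6.1.6).
- Abstinence, where chosen: from 14 days before Visit 1 onward (Section 4.1).

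**Assumption.** The documents give no lag between conception and a positive urine test. I take L = 10, 14 or 21 days.

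**Step 1: last test to first possible VVN001 dose.** 14 − 2 = 12 and 14 + 2 = 16 days. Appendix 1 and SAP Table 1 instead print Visit 1 as Day −14 ± 1 and Visit 2 as Day 1 ± 2. With no Day 0, that gives 13-15 days (Visit 1 window alone) or 11-17 days (both windows). With a Day 0, it gives 14-16 or 12-18 days. Every reading leaves at least 11 days. A Visit 2 test makes the interval 0.

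**Step 2: gap between the two scheduled tests.** Visit 2 to Visit 6 is 82 − 1 = 81 to 86 − 1 = 85 days. Adding R gives 81 + 12 = 93 to 85 + 16 = 101 days, or less with early termination.

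**Step 3: non-abstinent women.** Conceptions undetected at first dose span R + L days now and L days with a Visit 2 test. The share removed is R/(R + L). Run-in conceptions that a Visit 2 test could detect span max(0, R − L) days.

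| L (days) | Now, R + L | With Visit 2 test | Share removed | Run-in days detectable |
|---|---|---|---|---|
| 10 | 22-26 | 10 | 12/22 to 16/26 = 55-62% | 2-6 |
| 14 | 26-30 | 14 | 12/26 to 16/30 = 46-53% | 0-2 |
| 21 | 33-37 | 21 | 12/33 to 16/37 = 36-43% | 0 |

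The reduction is R = 12-16 days in every row. Most of what the test catches are conceptions shortly before Visit 1, not during the run-in.

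**Step 4: abstinent women.** A conception before the abstinent period is missed at Visit 1 over max(0, L − 14) days: 0, 0 and 7 days for the three lags. At L = 21 the gap covers conceptions 14 to 21 days before Visit 1. A Visit 2 test detects those earlier than L − R = 21 − 16 = 5 to 21 − 12 = 9 days before Visit 1, so it closes the whole gap.

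**The case against.** The strongest reply is that this is a consistent scheduling choice. Continuing to meet a criterion does not mean re-measuring it, and dilated ophthalmoscopy and the safety laboratory tests are not repeated at Visit 2 either. Both documents agree on Visits 1 and 6. Other controls exist: abstinence or birth control under inclusion 5, the Visit 2 eligibility review, discontinuation for pregnancy (Section 5.1), and freedom to perform an unscheduled test (Section 6.1.8). The window figures rest on an assumed lag and count calendar days, not pregnancies. For abstinent women the gap is zero at two of the three lags.

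There is also a fair point about the denominator. Conceptions during treatment can lead to exposure too. Over the whole span of L + R + 81 to 85 days, a Visit 2 test removes from 12/(21 + 12 + 85) = 10% to 16/(10 + 16 + 81) = 15%. It does nothing for the treatment period itself.

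Much of this stands as a limit on size. The sections do not contradict one another, the percentages depend on the lag, and the number of exposures prevented cannot be estimated and could be very small. The gap itself remains. The controls are partial, nothing requires a test before the first active dose, and the plan already uses testing alongside contraception at Visits 1 and 6.

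**Conclusion.** The concern holds. A plan followed exactly as written could randomize, and expose to VVN001, a woman whose pregnancy a same-day test would have shown. Under Section 6.1.2 the last result is 12-16 days old at the first possible VVN001 dose, and it is at least 11 days old under any printed window. That finding needs no assumption beyond the visit windows.

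The reduction of 12-16 days in the span of undetected conceptions, about 36-62% of the pre-dose window, applies to non-abstinent women and assumes a lag of 10 to 21 days. For abstinent women there is a benefit only if the lag exceeds 14 days. The documents give neither the number of women of childbearing potential nor a conception rate, so no expected count can be stated. Efficacy endpoints, power and type I error are not affected. The change should be made because it is cheap and serves participant safety.

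**What to change.** - **Protocol Section 6.1.2:** add the urine pregnancy test already used at Visits 1 and 6, for women of childbearing potential, with the result available before IWRS entry and the first double-masked dose.
- **Protocol Appendix 1 and SAP Table 1:** mark Visit 2 in the pregnancy test row.
- **SAP Section 4.8.3:** state that results are captured at Visits 1, 2 and 6. Listing 16.2.8.1 can hold the extra result, so no new output is needed.

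The cost is one urine dipstick per woman of childbearing potential at an existing visit, one added protocol line, one cell in each schedule table and one edited SAP sentence. No visit or staff is added. Very recent conceptions will still be missed at Visit 2, and the interval from Visit 2 to Visit 6 stays as it is.
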